1.19 STUDY INTERVENTION COMPLIANCE

The loading dose will be given prior to discharge. The remaining study drug will be taken as an outpatient over the next 6 days. We will ask participants to complete a study drug log to record timing of each dose. We will not plan any labs or assays for verification. Drug log will be collected at the first outpatient visit.

1.20 CONCOMITANT THERAPY

Concomitant medications will not be restricted. No change from standard post-head injury care will be implemented, other than use of the study drug or placebo. Concomitant medications will be recorded. For this protocol, a prescription medication is defined as a medication that can be prescribed only by a properly authorized/licensed clinician. Medications to be reported in the Case Report Form (CRF) are concomitant prescription medications, over-the-counter medications and supplements.

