1.6.3 ASSESSMENT OF POTENTIAL RISKS AND BENEFITS

Existing evidence is consistent with a very positive risk to benefit assessment. Prior clinical trial with the exact NAC regimen in TBI patients reported no adverse effects. The treatment involves only a 1 week course of therapy. There are no existing alternatives. Basic science studies provide a wealth of evidence for promoting neuronal recovery using this drug.

OBJECTIVES AND ENDPOINTS

OBJECTIVES		ENDPOINTS		JUSTIFICATION FOR ENDPOINTS		
Primary						
To determine if early treatment with NAC after head injury results in improved olfactory function, compared to placebo.		1.6.3.1.1.1.1	Olfactory function at 1 and 3 months post- enrollment, as measured by Smell Identification Test (SIT).	1.6.3.1.1.1.2	sIT is a validated test for olfaction. Time points of 1 and 3 months were chosen to test for early recovery of olfactory neurons versus evidence for successful regeneration, respectively.	
Secondary						
1.6.3.1.1.1.3	To assess olfactory- specific quality of life measure in treated versus placebo groups.	1.6.3.1.1.1.4	Questionnaire on olfactory dysfunction (QOD) scores at 1 and 3 months.	1.6.3.1.1.1.5	QOD is a validated tool for measuring quality of life related to olfactory loss.	

OBJECTIVES	ENDPOINTS	JUSTIFICATION FOR ENDPOINTS
Tertiary/Exploratory		
N/A		

STUDY DESIGN

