1.12 EXCLUSION CRITERIA

An individual who meets any of the following criteria will be excluded from participation in this study:

- 1. Severe trauma requiring ongoing inpatient treatment beyond 48 hours
- 2. Pregnancy (based on urine screening) or lactation
- 3. Known allergic reactions to components of NAC, such as Mucomyst
- 4. Currently taking nitrates such as nitroglycerine and/or isosorbide regularly
- 5. Currently taking azathioprine (Imuran) or cyclophosphamide (Cytoxan)
- 6. Known diagnosis of cystinuria (renal condition in which cysteine supplement should be avoided)
- 7. Febrile illness within 1 week
- 8. Treatment with another investigational drug or other intervention within 3 months
- 9. Active sinonasal disease by imaging and/or nasal exam, i.e. rhinosinusitis, nasal polyps
- 10. Adults unable to consent
- 11. Prisoners, employees or subordinates
- 12. Individuals who are not yet adults (infants, children, teenagers). This population is excluded because efficacy has not yet been established in adults.

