1.16 STUDY INTERVENTION(S) ADMINISTRATION

1.16.1 STUDY INTERVENTION DESCRIPTION

Subjects will be randomized to receive either N-Acetyl-Cysteine (NAC) or placebo, to be prepared and packaged by our research pharmacy. NAC will be administered orally as a 4 gram loading dose, followed by 2 g PO BID for 4 days, then 1.5 g PO BID for 2 days.

NAC is available as a generic over-the-counter oral supplement. It is not FDA regulated. Since there is **not** an FDA-approved labeling for over-the-counter oral NAC use, our trial does not change any existing label. NAC is also the active ingredient in the drug Mucomyst. Mucomyst is used as a pulmonary inhaled nebulized drug for its mucolytic properties to help treat chronic bronchitis. NAC is also administered orally or by nasogastric tube in Emergency Departments for the treatment of acetaminophin (Tylenol) overdose.

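### Placebo participants may take over-the-counter NAC within the rules, so the SIT difference may be diluted and power may fall below 0.8

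*Combined protocol and SAP*

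**What the plan says.** Availability (1.16.1): "NAC is available as a generic over-the-counter oral supplement".

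Concomitant therapy (1.20): "Concomitant medications will not be restricted". The same section sets what is recorded: "Medications to be reported in the Case Report Form (CRF) are concomitant prescription medications, over-the-counter medications and supplements". The schedule of activities (1.3) puts a medication review at screening, at Day 0 and at the two follow-up visits.

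Exclusions (1.12): the only criterion that names NAC concerns allergy, "Known allergic reactions to components of NAC, such as Mucomyst". The nearest criterion on prior treatment is number 8: "Treatment with another investigational drug or other intervention within 3 months".

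Other sections: lifestyle considerations (1.13) are marked not applicable. The dosing (1.16.2), compliance (1.19) and withdrawal (1.22) sections say nothing about NAC from outside the trial. On exposure, 1.19 says "We will not plan any labs or assays for verification". Section 1.6.1 says patients will be counselled that the usual care for this condition is no treatment.

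Analysis (1.31.1 to 1.31.3): SIT and QOD scores are compared between arms by two-tailed t-test. Reported use of outside NAC plays no part.

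**The concern.** The trial compares NAC with no NAC. When the test drug can be bought freely and the protocol allows any concomitant medication, nothing in the protocol text keeps the placebo arm free of it. Participants know they may be on placebo and are told that usual care offers nothing, so some may plausibly buy it. That step is an inference; the documents report no such use.

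Placebo-arm use would turn the comparison into NAC against partial NAC. If NAC has an effect, the expected SIT difference shrinks and power drops. The risk is a missed benefit, not a false positive. Self-report at the medication reviews could show that it happened, but the plan does not say what would follow.

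**Working it through.** **Inputs.** Section 1.29: placebo mean 17, NAC mean 25, SD 10 in each arm, alpha 0.05, power 0.8, 30 per arm. Section 1.31.2: two-tailed t-test. Section 1.29 also adds five per arm for dropout, withdrawal, missing data and the like; contamination is not named. Placebo-arm uptake of outside NAC is not in the documents, so 5%, 10% and 20% are assumptions.

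**The plan's own figure.** With a difference of 25 − 17 = 8:

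n per arm = 2 × 10² × (1.960 + 0.842)² / 8² = 24.5, rounded up to 25; 25 + 5 = 30.

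This matches the stated size. The exact t-test needs 25.5, so 26. Its power is 0.791 at 25 per arm and 0.861 at 30 (normal approximation: 0.807 and 0.873). The sample size is not in error.

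**Dilution model.** Let a fraction f of placebo participants take outside NAC and gain e points, with no added effect in the NAC arm. Then:

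- expected difference D = 8 − e·f
- placebo variance V = 100 + e²·f·(1 − f), because the arm becomes a mixture
- standard error = √[(100 + V)/n]
- power from the noncentral t with 2n − 2 degrees of freedom and noncentrality D / standard error.

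**Worked case.** For f = 0.10, e = 8 and n = 30: D = 8 − 0.8 = 7.2; V = 100 + 64 × 0.10 × 0.90 = 105.76; standard error = √(205.76/30) = 2.619; noncentrality = 7.2/2.619 = 2.75; power = 0.771.

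**Power by assumed uptake**

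| Gain in users | n per arm | f = 0 | 5% | 10% | 20% |
|---|---|---|---|---|---|
| Full, 8 points | 30 | 0.861 | 0.819 | 0.771 | 0.662 |
| Full, 8 points | 25 | 0.791 | 0.743 | 0.691 | 0.580 |
| Half, 4 points | 30 | 0.861 | 0.843 | 0.822 | 0.778 |
| Quarter, 2 points | 30 | 0.861 | 0.853 | 0.843 | 0.824 |

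In the full-effect rows the expected difference is 7.6, 7.2 and 6.4 points. In the half-effect row it is 7.8, 7.6 and 7.2.

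**Does any exclusion close the gap?** Criterion 3 is about allergy. Criterion 8 might be read to include a supplement taken earlier, but it does not say so and looks only at the period before entry. Neither limits NAC bought after discharge.

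**The case against.** The strongest reply is that the risk is unquantified and the full-effect figures are generous to it. The regimen totals 4 + (2 × 2 × 4) + (1.5 × 2 × 2) = 26 g over about a week. The design rationale (1.8) is that benefit depends on treating early. For 20% full-effect uptake, 6 of 30 placebo participants would have to obtain comparable exposure in that window while already taking blinded capsules. Later or smaller doses should dilute less. This stands: the full-effect rows are upper bounds at each uptake level, and at a quarter of the effect power stays above 0.8 throughout.

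Supplements are also recorded and reviewed at four visits. That stands as partial monitoring, but it neither prevents use nor feeds any analysis. The consent form is not in the public text and may carry an instruction on supplements; if so, 1.20 still needs to agree with it.

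Three stronger readings are tempting and not supported:

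- A reader might infer that power necessarily falls below 0.8. At 30 per arm and 5% full-effect uptake it is 0.82, so it may fall below, no more.
- A reader might take "There are no existing alternatives" in 1.6.3 as something participants are told. It is the sponsor's own risk-benefit assessment. The participant-facing statement is the counselling in 1.6.1, and any motive to buy NAC is inferred from that.
- A reader might see a contradiction between the open rule in 1.20 and drug exclusions such as "Currently taking nitrates such as nitroglycerine and/or isosorbide regularly". Section 1.22 largely answers this: the investigator may withdraw a participant who newly meets an exclusion criterion.

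**Conclusion.** The gap is real. The protocol says the test drug is freely sold, restricts no concomitant medication, and has no exclusion that clearly covers NAC use. If NAC works, any placebo-arm use biases the SIT difference toward zero.

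The size is unknown because the documents give neither uptake nor outside dose. Under the assumed uptake of 5% to 20%, power at 30 per arm lies between 0.82 and 0.66 if users gain the full effect, and between 0.84 and 0.78 if they gain half. If losses leave 25 evaluable per arm, power is 0.79 before any dilution and 0.74 to 0.58 with full-effect use, so no margin remains. These figures rest on the plan's 8-point difference and SD of 10.

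No stated figure in the plan is wrong. This is a design weakness worth closing because it is cheap to close.

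**What to change.** 1. In 1.12, add current use of non-study NAC supplements as an exclusion that applies at screening only. If it also applied after entry, the newly-met-exclusion rule in 1.22 could be used to withdraw participants who self-supplement.
2. Reconcile 1.20 with the comparison the trial makes by excepting the study drug from the open rule. Participants agree not to self-supplement with NAC during follow-up; NAC given for medical need is unaffected and is recorded.
3. Ask about non-study NAC by name at the medication reviews already in the schedule, and report use by arm. Where a visit is replaced by post (1.26.8), the described mailing holds only the SIT and the QOD, so the question must be added to it.
4. In 1.22, state that non-study NAC use alone does not lead to withdrawal, replacement or removal from the analysis, so users stay in their randomised arm. Without this, the request in item 2 could be treated as non-compliance. Section 1.22 allows withdrawal for significant non-compliance and has withdrawn treated participants replaced.

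Cost: one exclusion line, one exception in 1.20, one sentence in 1.22 and one question at existing contacts. A few current NAC users become ineligible. The study regimen does not change.

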1.6 RISK/BENEFIT ASSESSMENT

1.6.1 KNOWN POTENTIAL RISKS

Risks from medication: NAC is FDA approved, with a forty-year safety history. It is widely used for nebulized delivery to the lower airways for its mucolytic effects (Mucomyst). Otolaryngologists have prescribed NAC off-label as a topical nasal medication for years for certain chronic rhinosinusitis patients for it mucolytic effects, with no safety concerns reported. It also has a long history of systemic oral administration safely. It is used at high dose orally in emergency departments for acetaminophen overdose, to prevent hepatotoxicity. Known side effects reported from nebulized pulmonary delivery include some patients reporting a noticeable odor. Other possible side effects might include local irritation; however it has been used widely in the lower airways and via tracheostomy stoma without irritation. There are rare reports of bronchospasm reactions to NAC delivered to the lower airways via nebulizer; these typically respond to bronchodilators (albuterol). Loading doses for FDA-approved oral administration of NAC are about 55 ml of 20% NAC solution (≈10 g), and our study patients will receive a 4 g loading dose, much lower. Importantly, a recent published study using the identical oral NAC regimen proposed here reported no adverse events or treatment side effects³. NAC can cause headache or potentiate effects of nitroglycerine or isosorbide. It may alter levels of homocysteine. It may potentiate the effects of certain immunosuppressants, such as cyclophosphamide or azathioprine. It can cause GI upset.

Other risks: There is no economic risk, as we will supply the study medication. The pre-study work up and care is the trauma standard-of-care, unchanged, and is no different for patients choosing or not choosing to participate in this study. Psychologically, there is the risk of disappointment from possible lack of improvement or from treatment with placebo. However, the current standard-of-care is **no treatment**, so we will council patients regarding this.

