1.16.2 DOSING AND ADMINISTRATION

NAC or placebo will be administered orally as a 4 gram loading dose, followed by 2 g PO BID for 4 days, then 1.5 g PO BID for 2 days. The loading dose will be given prior to discharge from Ryder Trauma center. Remaining doses will begin on the following morning as an outpatient to complete the 1 week treatment course. Delayed doses may be taken late if noted before the next dose, and otherwise will be skipped. The doses may be taken with or without meals.

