1.22 PARTICIPANT DISCONTINUATION/WITHDRAWAL FROM THE STUDY

Participants are free to withdraw from participation in the study at any time upon request.

An investigator may discontinue or withdraw a participant from the study for the following reasons:

- Pregnancy
- Significant study intervention non-compliance
- If any clinical adverse event (AE), laboratory abnormality, or other medical condition or situation occurs such that continued participation in the study would not be in the best interest of the participant
- If the participant meets an exclusion criterion (either newly developed or not previously recognized) that precludes further study participation

The reason for participant discontinuation or withdrawal from the study will be recorded on the NAC Case Report Form (CRF). Subjects who sign the informed consent form and are randomized but do not receive the study intervention may be replaced. Subjects who sign the informed consent form, and are randomized and receive the study intervention, and subsequently withdraw, or are withdrawn or discontinued from the study, will be replaced. Patients who do not complete the full course of study drug/placebo will be noted in the results tables, and they will not be included in the statistical analysis of outcome measures, since this is a simple comparison of SIT score between patients receiving a 1 week course of NAC versus placebo.

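### Exclusion 4 bars only regular nitrate use and section 1.20 restricts no drug, so an as-needed nitrate user may take nitrates with NAC on Days 0–6, a combination section 1.6.1 names as a risk

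*Combined protocol and SAP*

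**What the plan says.** **The risk.** Section 1.6.1 states: "NAC can cause headache or potentiate effects of nitroglycerine or isosorbide". On immunosuppressants it adds: "It may potentiate the effects of certain immunosuppressants, such as cyclophosphamide or azathioprine".

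**Entry.** In section 1.12, exclusion 4 reads "Currently taking nitrates such as nitroglycerine and/or isosorbide regularly". Exclusion 5 bars anyone currently taking azathioprine or cyclophosphamide and carries no qualifier about regularity.

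**During treatment.** Section 1.20 says "Concomitant medications will not be restricted". It has concomitant drugs recorded, and it adds "No change from standard post-head injury care will be implemented, other than use of the study drug or placebo".

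**Exposure.** Under section 1.16.2 the loading dose is given before discharge, and then "Remaining doses will begin on the following morning as an outpatient to complete the 1 week treatment course". The schedule of activities (1.3) places home treatment on Days 1–6.

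**Backstops.** Section 1.22 lists situations in which an investigator may withdraw a participant. One is "If the participant meets an exclusion criterion (either newly developed or not previously recognized) that precludes further study participation". Another covers any adverse event, medical condition or situation that makes continuing contrary to the participant's best interest. Section 1.21 stops study drug when a patient notes a possible adverse effect.

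**The concern.** The sponsor judged the nitrate interaction important enough to list as a risk and to use as a reason for exclusion. The entry criterion and the on-treatment rule do not carry that judgement through. Exclusion 4 reaches only habitual users, and 1.20 places no limit on what may be taken with study drug. A site that follows the text exactly could enrol someone who carries a nitrate for occasional use, and that person could take it on any dosing day.

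New starts during dosing are a lesser part of the same gap. Section 1.20 also permits a newly prescribed nitrate, azathioprine or cyclophosphamide, and 1.22 allows withdrawal in that case but does not require it.

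What is at stake is the safety of a few participants and clear instructions for the site. The trial's inference is not at stake.

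**Working it through.** The plan states no figure on this point, so the check is mainly a reading of the sections against each other.

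1. **Is the interaction a named risk?** Yes, in 1.6.1. The text does not limit it to regular nitrate use and gives no severity.
2. **Does any entry criterion exclude an as-needed user?** Exclusion 4 is limited by the word *regularly*; exclusion 5, the next line, has no such limit. No other item in 1.11 or 1.12 concerns nitrates, and entry is open from age 18 with no upper limit.
3. **Does any rule apply during dosing?** Section 1.20 restricts nothing, lifestyle considerations (1.13) are not applicable, and the dosing text (1.16.2) contains no nitrate rule.
4. **Would the use be noticed?** The schedule in 1.3 has medication review at screening, Day 0, Visit 2 and Visit 3. The Days 1–6 column shows only study drug administration.
5. **Do the backstops close the gap?** The newly-met-exclusion bullet of 1.22 does not reach as-needed nitrates, because such use is not an exclusion. The best-interest bullet can reach it, but it is at the investigator's discretion and requires the use to be known. Section 1.21 acts only after a possible adverse effect has been noted.

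**Dosing arithmetic** (inputs: regimen in 1.16.2, visit windows in 1.3). These figures describe the schedule for every participant and do not measure risk.

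- Administrations: 1 + 4 × 2 + 2 × 2 = 13, of which 12 are at home; 12/13 = 92%.
- Dose: 4 + 4 × 2 × 2 + 2 × 2 × 1.5 = 4 + 16 + 6 = 26 g, of which 22 g is at home; 22/26 = 85%.
- Next medication review after the last dose on Day 6: Visit 2 at Day 30 ± 7, that is Day 23 to 37. 23 − 6 = 17 days and 37 − 6 = 31 days.

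**Cost of the fix** (inputs: 1.15 and 1.29): 300 screened / 60 enrolled = 5 screened per participant.

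**The case against.** The strongest reply is that *regularly* was chosen on purpose. Section 1.6.1 says NAC can have this effect; it does not call the combination contraindicated. Excluding habitual users while accepting occasional use over a one-week course is a defensible threshold. That may have been the intention, but the plan gives no reason for it. If occasional use is acceptable, 1.20 should say so and say what happens to study drug when a nitrate is taken. At present it is silent on that.

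The other safeguards also deserve their weight. Medication is reviewed at screening and on Day 0, nursing staff give the loading dose, and section 1.25 tells patients to contact the team promptly about problems. These reduce the concern, but neither review gives the site a reason to turn away or instruct an as-needed user.

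The unchanged-standard-care sentence in 1.20 is a sound reason not to withhold a needed drug. It does not settle whether study drug continues.

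A reader might infer three stronger points that the documents do not support:

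- **That nothing in the plan could act.** The best-interest bullet of 1.22 can reach nitrate use, the newly-met-exclusion bullet can reach new starts, and 1.21 covers a symptomatic interaction.
- **That patients are not warned.** The discharge instructions (1.17.1, 1.25) and the consent form (1.32.1.1) are not part of the text available here and may already name these drugs.
- **That the 92% or 85% shows a large hazard.** Those are shares of the dosing schedule, not of people exposed to nitrates.

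**Conclusion.** The inconsistency is real and minor. As written, the plan admits as-needed nitrate users and lets them take nitrates with NAC on Days 0–6, although 1.6.1 lists that interaction as a risk. The safeguards that remain are discretionary or reactive, and no medication review falls within home dosing.

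Its size cannot be given. The documents report no rate of as-needed nitrate use or of new starts, and no severity. Only the planned 30 NAC participants could experience the interaction; a single such user would be 1/30 = 3.3% of that arm, which is the weight of one person and not an expected rate. Type I error, power and the SIT endpoint are unaffected.

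The conclusion rests on two readings: that *regularly* in exclusion 4 leaves out as-needed use, and that the Days 1–6 column of the schedule contains no medication review.

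**What to change.** 1. **Exclusion 4 (1.12).** Change it to: *currently taking nitrates, regularly or as needed*. Ask about as-needed nitrates at the existing screening and Day 0 medication reviews.
2. **Section 1.20.** Amend to: *Concomitant medications are unrestricted, except that nitrates (including as-needed), azathioprine and cyclophosphamide should not be taken with study drug from the loading dose to the last home dose. If one is clinically needed it is not withheld; the participant stops study drug and contacts the study team.* Keep the two sentences together. A ban without the second sentence could delay a needed treatment.

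**Cost.** A few words in 1.12 and two sentences in 1.20, with no new visit. A few as-needed nitrate users become ineligible, at about 5 more people screened for each participant replaced. Because the trial is blinded, a rare participant in either arm may stop study drug early, including someone on placebo who faces no interaction.

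**A linked matter to settle separately.** Section 1.22 leaves anyone who does not complete the course out of the outcome analysis, while 1.30 defines an intention-to-treat set of all randomised participants. Until that conflict is resolved, an early stop under the new 1.20 would remove 1 of 30 (3.3%) from an arm. Resolve it for all participants. A carve-out for people who stop because of a nitrate would keep them in the analysis while others who stop early are still dropped.
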